3. A limited control set using listening to oral reading of the lyrics and silent reading of the written lyrics with observation of pointing to written lyrics (no music).

Dependent Variables:

The dependent variable was defined as silent reading/comprehension of targeted words/phrases by pointing to words/phrases in a phrase completion exercise without music. The dependent variable was kept constant for all three conditions.

Dependent Measures

Measurement of the dependent variable consisted of both direct systematic observational recording (DSOR) and treatment record video (for reliability/procedural fidelity assessment) of percentage correct over time (including follow-up) and trials- or sessions-to-criterion.

Research Design

An AATD was used for comparison of two separate but similar conditions when the effects may be non-reversible (see Gast & Ledford, 2014, pp. 324-332). Time between sessions was at least a day.

“Criteria:

1. Behaviors must be non-reversible—the behaviors will continue to be performed after instruction has stopped.
2. Behaviors should not be in the participants' repertoire.
3. Behaviors must be independent, meaning one behavior set/chain can be acquired without influencing performance on other behavior sets/chains.
4. Behaviors also must be functionally equivalent, meaning behaviors are likely to be influenced by the same environmental variable (e.g., the instructional strategies being studied).
5. *Behavior sets/chains must be of equal difficulty.* The dependent variable in this investigation will be phrases acquired, but three different sets will be required to fulfill the requirement that the behaviors are independent. To ensure that they are of equal difficulty, they must all be assessed for word complexity at a minimum.

Randomizing items between treatment conditions should result in a relatively equal distribution of difficulty” (Romer, Billingsley, & White (1988).

Procedures

All songs were pretested for familiarity and positive valence by questioning the participants (i.e. Do you know this song? Do you like it?). Response data was recorded. All songs perceived as not liked were eliminated and substitutions made; the new songs were then also pretested for familiarity and positive valence. Songs that were not familiar but were liked were noted but not changed.

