During the baseline (A) all 25 phrases (Appendix C) were tested using the phrase completion task (Appendix D). Both correct responses and participation were verbally reinforced, as is required in an AATD. Results were analyzed by the SLP to ensure that the sets were of equal difficulty for each participant using two different procedures. First, logical analysis of the linguistic characteristics of the phrases was completed, including the number of words, the number of syllables in the words, the number of consonant blends in the words, and the number of contractions. Second, experimental evaluation of the number of error responses in each set during the baseline phase was completed, and without changing the items or responses, the set assignment was manipulated to maximally equate the number of error phrases without significantly changing the equivalency of the linguistic characteristics. One phrase was shifted from set 1 to set 2 during the baseline phase. In the end, the number of error responses on baseline for set 1 was three, for set 2 was two, and for the control set was two.

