During the intervention (B), each song (music with lyrics) from set 1 (B1) was played in its entirety. When the targeted verse or chorus played, the written lyrics were simultaneously shown along with the song lyrics. The SLP pointed to the words of the targeted verse/chorus which was silently observed by the participant as they were sung. This was repeated for all ten songs. The phrase completion task was then presented, including the total 25 phrases, without music. The participant silently or orally read the phrase and circled the phrase completion choice. Correct responses were randomly verbally reinforced. Error responses were followed by verbal modeling and pointing to the correct choice by the SLP. The next session, each song (music with lyrics) from set 2 (B2) was played in its entirety. After the song played, the written lyrics from the targeted verse or chorus were presented. The SLP pointed to the words of the targeted verse/chorus which was silently observed by the participant. This was repeated for all ten songs. The phrase completion task was then presented, including the total 25 phrases. The participant silently or orally read the phrase and circled the phrase completion choice. Correct responses were randomly verbally reinforced. Error responses were followed by verbal modeling and pointing to the correct choice by the SLP. This was repeated for all ten songs. For all interventions, the number of correct responses were tallied on a LaPoint Base 10 form and the percent correct entered on the graph for that day. The same procedures were repeated, alternating procedures on sets 1 and 2 on subsequent treatment visits, until a criterion of 9/10 (90%) x 3 consecutive visits was reached on both sets. It was predetermined that if the criterion was not reached on one of the intervention sets, defined as no increase in percentage correct x 3 consecutive visits, that intervention would be considered to be limited in effectiveness and discontinued. Every third session was digitally recorded for a reliability check by the trained assistant. When both of the sets (B1 and B2) had been acquired or one acquired and the other discontinued, the number of sessions to criterion were counted for each intervention.

Potential Threats to Internal Validity

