Potential threats to internal validity included multiple-treatment interference in the form of sequential confounding and carryover effects. Counterbalancing conditions was necessary, and any carryover effects identified (see Gast & Ledford, 2014, chapter 5 p.101). Because AATD studies test efficiency, the goal involves demonstrating optimal performance as opposed to artificially deflated performance, so responses were reinforced during the baseline phase (see Gast & Ledford, 2014, p. 326).

Potential threats to internal validity also included possible history or maturation effects. A control set was used to rule out history and maturation effects.

Outcome Measures and Time Points

Pretest/post-test information on the ICF Body Functions/Structures, Activities, and Participation was provided (Hurkmans et al. 2011). The Boston Diagnostic Aphasia Examination (BDAE) (Goodglass, Harold, & Kaplan, 1983) was used as an outcome measure of reading acquisition. The BDAE is a classic anatomically-based diagnostic instrument. Because various components of language function may be selectively damaged by CNS lesions, results indicate the neuro-anatomical organization of language and localization of the lesion. Thus it serves as an appropriate assessment for research exploring neurological organization in the brain. Pretest reading scores on selected subtests from the BDAE full version were completed prior to baseline A and initiating intervention, and immediately following completion of intervention to assess generalization to non-trained stimuli. At four weeks follow-up the trained stimuli from all three interventions was retested to assess retention. The dependent variables, that is differential response to the two interventions (counted as the percent correct responses per day, a ratio scale which has equal intervals and an absolute zero, which allows for multiplication and division so is appropriate for averages), number of sessions required to achieve mastery at each level (simple counting but also a ratio scale as it has equal intervals and an absolute zero which allows for multiplication and division so allows for the difference between means), retention of the material (number of items remembered, another simple count which is also a ratio scale as it has equal intervals and an absolute zero and allows for the difference between means), was assessed using data analysis as described below.

Data Analysis

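### The outcome is defined as silent reading held constant, but the intervention-phase tests allow silent or oral reading, and no section fixes or records which was used.

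*Combined protocol and SAP*

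**What the plan says.** The Dependent Variables section gives the outcome as "silent reading/comprehension of targeted words/phrases by pointing to words/phrases in a phrase completion exercise without music" and adds: "The dependent variable was kept constant for all three conditions".

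The Procedures section, describing the test that follows each intervention session, says: "The participant silently or orally read the phrase and circled the phrase completion choice". The sentence appears twice in the same words, once for the simultaneous-music condition (B1) and once for the priming condition (B2). On what is tested, it says: "The phrase completion task was then presented, including the total 25 phrases, without music". The control phrases are thus tested under the same permission.

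The same section reports that all 25 phrases were also tested at baseline, without giving a reading mode. Outcome Measures and Time Points is equally silent on mode for retention: "At four weeks follow-up the trained stimuli from all three interventions was retested to assess retention".

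On what is written down at each visit, Procedures says that "the number of correct responses were tallied on a LaPoint Base 10 form and the percent correct entered on the graph for that day". No field for reading mode is described.

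**The concern.** Reading a phrase aloud and reading it silently are not the same task. A participant who reads aloud also hears the words. Here the trained material is song lyrics and the test asks for a lyric phrase to be completed, so hearing the phrase might help in a way that print alone does not. The documents neither measure nor discuss this.

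The score that might be affected feeds almost everything: percent correct per visit, sessions to criterion, the rule for discontinuing a condition, the comparison of intervention points with the two-standard-deviation band from baseline, and retention. If mode differed between baseline and intervention, or drifted over visits, the graph would show a change that is partly a change of task. A reader could not separate the two, because mode does not appear in the described record.

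**Working it through.** The plan gives no figure on this point, so there is none to reproduce. The check sets the sections side by side.

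**1. Mode and response act, by administration**

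| Where | Reading mode | Response act |
|---|---|---|
| Definition (Dependent Variables) | silent | pointing |
| Baseline test (Procedures) | not stated | not stated |
| Test after B1 (Procedures) | silent or oral | circling |
| Test after B2 (Procedures) | silent or oral | circling |
| Control phrases at those visits (part of the 25) | silent or oral | circling |
| Retention test (Outcome Measures and Time Points) | not stated | not stated |
| Video description (Human Rights Protections) | not addressed | both pointing and circling |

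The definition and the intervention-phase procedure disagree on both columns. For baseline and retention there is a gap rather than a contradiction.

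**2. Could mode be recovered afterwards?** The described record is a count of correct answers. The reliability checks in Data Analysis score correct against incorrect, so two observers could agree fully while mode varied. Video covers every third session, shows only hands, and is deleted after viewing; audio is not mentioned. Unless mode was noted at the time, recovery looks unlikely.

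**3. Which comparisons could an unrecorded shift reach?**
- Baseline to intervention: the two-standard-deviation band comparison.
- Between intervention visits: trend, sessions to criterion, and the discontinuation rule.
- B1 against B2: only if mode varies by phrase, or if it follows the alternation of B1 and B2 visits. A change of mode for a whole visit touches every set tested that day.

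**4. Sensitivity of the criterion (illustration only).** The mastery criterion is 9/10 on three consecutive visits. Assume ten phrases in a set, the same probability p of a correct answer for each phrase, and independent phrases and visits. Then

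P(at least 9 of 10) = 10p⁹(1 − p) + p¹⁰, and P(three given visits all meet it) is the cube of that.

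At p = 0.80: 0.2684 + 0.1074 = 0.3758; cubed, 0.053. At p = 0.90: 0.3874 + 0.3487 = 0.7361; cubed, 0.399.

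| Assumed p | One visit | Three given visits |
|---|---|---|
| 0.70 | 0.149 | 0.003 |
| 0.80 | 0.376 | 0.053 |
| 0.85 | 0.544 | 0.161 |
| 0.90 | 0.736 | 0.399 |
| 0.95 | 0.914 | 0.763 |

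If mode moved p from 0.80 to 0.90, the three-visit chance would go from about 5% to about 40%. The values of p are assumed. The table shows that the criterion reacts strongly to modest changes in p; it says nothing about whether mode changes p.

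**The case against.** The best defence is that the conflict rests largely on one word. The defined outcome covers comprehension as well as silent reading, and the scored act, a marked choice counted right or wrong, is the same in either mode. The title speaks of reading comprehension, and Data Analysis calls the graphed measure multiple-choice reading comprehension; neither requires silence. The statement about constancy can fairly mean that the same 25-phrase task served all sets. Appendix D, which holds the task, is not in the text available, so any instruction printed there cannot be judged.

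Much of this stands. It shows that the score can still be interpreted as phrase completion. It does not remove the conflict with the definition, nor the absence of any stated rule or record for mode.

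A reader might also infer that oral reading favours the music sets. The documents do not support that. The permission is worded identically for B1 and B2 and covers all 25 phrases. The control condition includes hearing the lyrics read aloud, and errors on any phrase are followed by verbal modelling, so control phrases are heard too. Memory of a song could also complete a line read silently.

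Nor can one say, from the baseline error counts of three in set 1 and two in set 2, that two or one phrases gained by reading aloud would secure mastery. Set sizes are not stated, a phrase was moved between sets, it is unclear whether the counts are per session or for the whole phase, and the criterion needs three consecutive visits.

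**Conclusion.** The point holds as a mismatch between definition and procedure. The outcome is named as silent reading shown by pointing and said to be constant; the intervention-phase tests allow either reading mode with a circled answer; mode is unstated at baseline and retention and, in the text available, is neither fixed nor recorded. Following the plan can yield a mixed-mode score labelled as silent reading, and an unrecorded change of mode could pass for a treatment effect.

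Its size is unknown. The illustration above rests on an inferred set size, independence and assumed probabilities, and cannot be turned into an estimate of bias. The documents do not show that a shift happened or in which direction it would act. It would go too far to conclude that the endpoint is invalid, or that mode was mixed at every test: oral reading is documented for the intervention phase only.

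The matter is still worth settling. Sample Size reports on the first two participants of a minimum of four, and Data Analysis plans group means once four have finished, so mixed modes could be averaged together without anyone being able to tell.

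**What to change.** Reconcile the Dependent Variables and Procedures sections, separately for future and past participants.

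*Participants still to be tested.* State one reading mode and one response mode for every administration: baseline, both interventions, the control set and follow-up. Where a participant departs from the stated mode, tick that phrase on the existing tally form. Keep all items in the score, because dropping ticked items would leave the 9/10 criterion undefined. Report how often each mode was used, by set and phase.

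*Participants already tested.* Leave the procedure text as performed; changing it to silent reading alone would misdescribe what the procedure allowed for them. Describe the outcome as phrase completion, that is, reading comprehension in either mode, and state whether mode was recorded. If it was not, report that as a limitation.

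The cost is small: a tick per item where needed, some reminders to participants during testing, and a somewhat narrower claim about which skill improved.

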A meta-analysis of studies using music for the treatment of neurological language and speech disorders showed that although measurable improvement was reported, the methodological quality of studies was rated low (Hurkmans et al., 2011). Specific recommendations were made to report education, dominance, and musical background, all of which were included in the current study. Education was reported based on highest level of formal education attained. Dominance was determined by premorbid handedness for writing. Musical background included reporting previous formal instruction for singing/choir, playing an instrument, or reading music, and experience with performance of singing, dancing, and listening to music.

Sample Size

A minimum of four participants was required to demonstrate replication of treatment effects (Gast & Ledford, 2014, p.327). A maximum of ten participants was requested from the Internal Review Board (IRB) to account for attrition. This study reports on the first two participants of the approved trials.

Environment

The physical environment was the Out-Patient Rehabilitation clinic in the ST office which is also a private treatment room (for Participant #2), and the patient's home when served by home health (for Participant #1). The clinic was located at the end of a hallway away from the other therapies so there was little noise or commotion. The SLP and client both sat at a large table with a minimum of materials laid out. The room was well-lit with no windows. Limited use of bright color added appeal without drawing undue attention. Distractions were kept to a minimum, but included training materials and a desk-top computer behind the therapist. All other materials were kept in a closed cabinet and filing cabinet. The patients and significant others were seated in various locations at the table to best accommodate vision and hearing. Home settings were controlled for lighting, sound, and undue distractions to the maximum extent possible.

Independent Variable:

The independent variable was manipulated to contrast three conditions:

1. Polyphonic music with song lyrics presented simultaneously with silent reading and observation of pointing to written lyrics (independent processing condition);
2. Priming with polyphonic music with lyrics followed by silent reading and observation of pointing to written lyrics (shared processing condition);

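### The baseline-to-intervention tests measure a package, not music alone, and the control set cannot exclude history and maturation unconditionally because it is itself practised, corrected and treated

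*Combined protocol and SAP*

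**What the plan says.** Procedures describes the two phases differently. At baseline all 25 phrases were tested, and "Both correct responses and participation were verbally reinforced, as is required in an AATD". Potential Threats to Internal Validity again says that baseline responses were reinforced. Neither place mentions correcting errors.

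For phase B, Procedures says "The phrase completion task was then presented, including the total 25 phrases, without music". The full set of 25 is also stated for the second music condition. For both conditions, "Correct responses were randomly verbally reinforced" and "Error responses were followed by verbal modeling and pointing to the correct choice by the SLP". No set is exempted. For scoring, "the number of correct responses were tallied on a LaPoint Base 10 form and the percent correct entered on the graph for that day". The schedule is "alternating procedures on sets 1 and 2 on subsequent treatment visits, until a criterion of 9/10 (90%) x 3 consecutive visits was reached", which applies to each music set. It does not mention the control set.

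Independent Variable gives the control set its own condition: hearing the lyrics read aloud and reading them silently while watching the pointing, without music. Outcome Measures and Time Points counts it as one of three interventions with trained items, and Data Analysis calls it a treatment.

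Data Analysis has two tests of change from baseline, the two-standard-deviation band and the split-middle binomial test. Neither uses the control set. A control comparison is planned only for sessions to mastery and for retention. Potential Threats to Internal Validity says without condition that the control set serves to exclude history and maturation. Assumptions and Limitations says the same of this type of design in general.

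**The concern.** If several things change when phase B starts, a test of phase B against baseline cannot say which of them produced the gain. As written, the music arrives together with repeated corrected testing of the same phrases, and either could teach them.

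The control set is the safeguard on offer, but it receives the same testing and correction and a reading condition of its own. Control phrases might rise because of spontaneous recovery, corrected practice or oral reading, and the plan does not say how a rise would be read. At stake is whether a significant band or binomial result may be reported as an effect of music, and whether recovery may be called excluded.

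**Working it through.** **Step 1. What differs between phases and between sets**

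| Component | Baseline | Phase B, music sets | Phase B, control set |
|---|---|---|---|
| Phrase task | all 25 | after every session | after every session |
| Error correction | not mentioned | yes | yes, no exemption |
| Reinforcement | correct responses and participation | correct responses, at random | same as music sets |
| Lyric reading with pointing | none described | yes | in the oral-reading condition, frequency not stated |
| Music | none described | yes | no |

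Baseline against music sets differs in music, lyric reading with pointing, reinforcement, the amount of testing and, if baseline errors were not corrected, correction. Music sets against control within phase B share testing, correction and reinforcement. They differ in music and, depending on how often oral reading was given, in lyric exposure and pointing. Each music set is also corrected on the other set's visits. The correction therefore dilutes the contrast between the two music conditions or brings an early ceiling, but does not favour one of them.

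**Step 2. Inputs for size**

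The plan has no power figure to reproduce: Sample Size gives a minimum of four participants from a cited text, with no effect size or SD. Procedures gives the error counts: "the number of error responses on baseline for set 1 was three, for set 2 was two, and for the control set was two". It does not say for which participant, although Sample Size says "This study reports on the first two participants of the approved trials". Set sizes are inferred from ten songs per music set and the 9/10 criterion: 10, 10 and 25 − 20 = 5.

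Reading the errors as distinct phrases, baseline correct is 10 − 3 = 7 of 10, 10 − 2 = 8 of 10 and 5 − 2 = 3 of 5. Set 1 is then 9 − 7 = 2 phrases short of criterion and set 2 is 9 − 8 = 1 short.

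**Step 3. How little change the phase tests need**

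- Binomial, one-tailed, flat baseline line assumed: 5 of 5 points above gives (1/2)^5 = 1/32 = 0.031; 7 of 8 gives (8 + 1)/256 = 0.035. One phrase learned from any cause and kept, with the others unchanged, puts every later point above the line.
- Band limit = mean + 2 SD, with an assumed baseline SD of 0, 0.5 or 1 phrase. For set 1 the limits are 7, 8 and 9, so 1, 2 or 3 newly correct phrases in two consecutive sessions exceed the band. For set 2 the limits are 8, 9 and 10, so 1 or 2 are needed, and at SD 1 the band cannot be exceeded.

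**Step 4. What the control contrast can show**

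If every error phrase is learned, the gain is 3/10 = 30 points (set 1), 2/10 = 20 (set 2) and 2/5 = 40 (control). Percentage points are therefore not comparable across sets.

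For one participant, the best case is that all music error phrases and no control error phrases are acquired. One-sided Fisher p, treating phrases as independent:

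- Set 1 v control, 3/3 v 0/2: 1/C(5,3) = 1/10 = 0.10
- Set 2 v control, 2/2 v 0/2: 1/C(4,2) = 1/6 = 0.17
- Both pooled v control, 5/5 v 0/2: 1/C(7,5) = 1/21 = 0.048

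These use only the error counts. If the counts are totals over several baseline sessions, there may be fewer distinct error phrases and every best-case p would be larger.

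**The case against.** The strongest reply has four parts.

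- *The baseline text is silent.* It never says that errors went uncorrected, and the descriptions of the two phases do not contradict each other. This stands. A reader might infer that correction certainly began with the music; the documents do not establish that. The rest of the package still changes at phase B, and the limit on the control set does not depend on it.
- *The main comparison is between the two music conditions, and correction does not bias it in one direction.* This also stands. Data Analysis, moreover, does not say in words that change from baseline is due to music alone. But it calls that change significant without saying what it can be attributed to, and its planned control comparison does not reach the session scores.
- *A flat control beside rising music sets is the usual logic of a control set.* Agreed. The objection is only to the lack of a condition.
- *The reading subtests of the aphasia battery, given before and after on untrained items, help to tell recovery from practice.* They help indirectly: recovery should raise untrained items too, but so could generalization from the trained phrases.

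The starting values are also fragile. The number of baseline sessions is not given, and one phrase was moved between music sets. If three errors were a total over three sessions, set 1 would average one error and start at 9/10. The figures are therefore illustrative, and the point rests on the text.

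**Conclusion.** The point holds in limited form. A significant band or binomial result describes the whole phase B package and does not by itself support a claim specific to music. The unconditional statement in Potential Threats to Internal Validity, and the general one in Assumptions and Limitations, are too strong for a control set that is tested, corrected and given oral reading.

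A reader might go further and infer that the control set is useless or that the study cannot address music at all. The documents do not support that. Correction is common to all sets, so the phase B contrast of music with control is not biased by it, and a flat control would be informative. That contrast isolates music only if control oral reading was given about as often as the music sessions.

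It is also thin. Within one participant its best-case one-sided p is 0.10, 0.17 or, pooled, 0.048, on the assumption that the 3, 2 and 2 errors are distinct phrases in that participant. The phase-test illustrations additionally assume sets of 10, 10 and 5 and the stated baseline SDs.

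**What to change.** 1. In Potential Threats to Internal Validity and Assumptions and Limitations, make the statement conditional: a flat control set beside rising music sets argues against history and maturation; a rising one cannot separate them from corrected practice or oral reading, and the untrained reading subtests help only indirectly.
2. In Data Analysis, state that the band and binomial results reflect the whole package. Base any claim specific to music on the phase B comparison of each music set, and of both pooled, with the control set, by extending the planned control comparison to the session scores. Report counts out of set size. Where phrase-level records exist, also report baseline-error phrases acquired and phrases newly missed. Treat the result as descriptive for each participant until the planned four-participant consolidation.
3. State how often the control oral-reading condition was given. If it was less often than the music sessions, say that the contrast reflects music plus extra lyric exposure and pointing.
4. The authors should clarify the baseline and phase B feedback descriptions, including whether baseline errors were corrected, and say whose error counts are reported. No feedback rule is proposed here.

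The cost is wording and re-tabulation, with no change to treatment, visits or staff. The limits are few error phrases per set and reliance on paper records, because the recordings were deleted. If the forms hold only tallies, or do not separate the sets, the report should say so.
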